21.5 Pregnancy Reporting

Certain information, although not considered an SAE, must be recorded, reported, and followed up as indicated. This includes the following:

Pregnancy exposure to an investigational medicinal product, except for exposure to prenatal vitamins. Subjects should not become pregnant during the study. If the subject becomes pregnant, study treatment must be discontinued immediately. The investigator must report the pregnancy by submitting the appropriate form to Mallinckrodt Global Pharmacovigilance or designee within 24 hours of confirmation of a pregnancy (ie, positive serum pregnancy test

result). The outcome of pregnancy (eg, spontaneous abortion, live birth, still birth, congenital anomalies, birth defects) must be reported by submitting the appropriate form to Mallinckrodt Global Pharmacovigilance or designee within 24 hours of the pregnancy outcome being submitted to the study site. If the pregnancy results in a live birth, a postdelivery follow-up will be performed at least 28 days after the baby is born and must be reported to Mallinckrodt Global Pharmacovigilance or designee within 24 hours of the study site becoming aware of the follow-up information. Both maternal and paternal investigational medicinal product exposures are collected.

If the female partner of a male subject becomes pregnant during the study, the site will forward the Pregnancy Notification Form and the Pregnancy Report Fax cover page to Mallinckrodt Global Pharmacovigilance or designee, within 24 hours of being notified. The outcome of pregnancy (eg, spontaneous abortion, live birth, still birth, congenital anomalies, birth defects) must be reported by submitting the appropriate form to Mallinckrodt Global Pharmacovigilance or designee within 24 hours of the pregnancy outcome being submitted to the study site. If the pregnancy results in a live birth, a postdelivery follow-up will be performed at least 28 days after the baby is born and must be reported to Mallinckrodt Global Pharmacovigilance or designee within 24 hours of the study site becoming aware of the follow-up information.

22 SUBJECT DISCONTINUATION OR WITHDRAWAL

22.1 Subject Withdrawal

Subjects who discontinue, or are withdrawn from the study for any reason, will be required to enter the follow-up period and have the Early Termination and Follow-up safety assessments to assess their continued well-being.

Subjects who early terminate for any reason other than withdrawal of consent should be encouraged to continue minimal study participation via telephone contact. In this circumstance, the ALSFRS-R should be administered over the telephone by the site, and any status update should be collected.

The reason for discontinuation will be recorded. A subject may be discontinued from the study for the following medical or administrative reasons:

Withdrawal by Subject

Subjects will be free to discontinue from the study at any time. Subjects who have received at least 1 dose of study drug but do not complete the study will not be replaced.

Investigator Judgment

If, in the opinion of the Investigator, the benefit/risk balance no longer favors continued study participation for any reason, the subject should be withdrawn.

Adverse Event

If a dosed subject suffers an AE that, in the judgment of the investigator, sponsor or MM, presents an unacceptable consequence or risk to the subject, the subject will be discontinued from further participation in the study.

Death

In the event that a subject dies during the study, death will be the reason for discontinuation.

Lost to Follow-up

Every effort should be used to maintain contact with subjects during their participation in the study. A subject may be considered lost to follow-up if there is no response to 3 attempts to reach the subject by telephone and no response to a certified letter sent to the last known address of the subject. Efforts to contact the subject should be noted in source documentation.

Met Withdrawal Criteria

If a subject is noncompliant (eg, has a positive pregnancy or drug screening test), the subject will be discontinued from further participation in the study. Discontinuation is also mandated for safety and/or tolerability issues as outlined in [Section 15.4.1](#).

Other

If the above reasons are not applicable, please use the “Other” option and provide the appropriate reason for subject withdrawal.

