15.4.1 Treatment Discontinuation

Subjects who early terminate for any reason must undergo the taper (2x/week for 2 weeks followed by 1x/week for 1 week) and should complete the End of Taper and Follow-up Visits.

Subjects who early terminate from the Randomized Treatment Period for any reason other than withdrawal of consent should be encouraged to continue minimal study participation via

telephone contact on a monthly basis if possible. In this circumstance, the ALSFRS-R should be administered over the telephone by the site, and any status update should be collected.

Treatment with study drug should be discontinued if any of the following occur:

- Development of accelerated hypertension (defined as systolic blood pressure ≥ 180 and diastolic blood pressure ≥ 100 mm Hg) that cannot be managed by the adjustment of concomitant medications such as antihypertensive medications.
- Development of congestive heart failure that cannot be managed by the adjustment of concomitant medications such as diuretics and antihypertensive medications.
- Development of diabetic signs/symptoms (ie, HbA1c $> 6.5\%$, or fasting plasma glucose > 126 mg/dL, or classic symptoms of hyperglycemia with random plasma glucose > 200 mg/dL) that cannot be managed by the adjustment of concomitant medications such as insulin and oral hypoglycemic agents.
- MedDRA System Organ Class infection/infestation of \geq moderate intensity.
- Hy's Law cases (ALT > 3 x ULN, with total bilirubin > 2 x ULN, no initial signs of cholestasis [alkaline phosphatase within the reference range]), and no other reason can be found to explain liver injury).

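### Section 22.1 ends participation for an unacceptable-risk AE, and most naturally for Section 15.4.1 drug stops; before about Week 28 the Week 36 ALSFRS-R then rests on encouraged telephone contact

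*Combined protocol and SAP*

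**What the plan says.** Section 22.1 introduces its list of exit reasons with "A subject may be discontinued from the study for the following medical or administrative reasons". Three entries matter here.

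- **Adverse Event.** The investigator, sponsor or medical monitor may make the judgment. If the event "presents an unacceptable consequence or risk to the subject, the subject will be discontinued from further participation in the study".
- **Met Withdrawal Criteria.** After a sentence on noncompliant subjects leaving the study, it adds: "Discontinuation is also mandated for safety and/or tolerability issues as outlined in" Section 15.4.1.
- **Investigator Judgment.** Withdrawal follows if, in the investigator's opinion, "the benefit/risk balance no longer favors continued study participation for any reason".

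Section 15.4.1 is headed Treatment Discontinuation, and its own rule is about the drug: "Treatment with study drug should be discontinued if any of the following occur". The criteria are accelerated hypertension, heart failure or diabetic signs that cannot be managed, infection of at least moderate intensity, and Hy's Law cases.

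Subjects who leave must taper over 3 weeks. Section 22.1 says they "will be required to enter the follow-up period and have the Early Termination and Follow-up safety assessments". Unless consent is withdrawn, they "should be encouraged to continue minimal study participation via telephone contact", with the ALSFRS-R given by telephone. Section 15.4.1 makes this contact monthly if possible and gives no end week.

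**The concern.** The primary endpoint (Section 20.3.1) is the change in telephone ALSFRS-R at Week 36. Stopping the drug for safety need not stop a telephone questionnaire, yet Section 22.1 ties the two together. A subject who is taken off drug moves from a fixed schedule to contact that may or may not happen, and may or may not reach Week 36.

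The missing scores could be related to treatment arm. Section 9.5 names raised blood pressure and altered glucose tolerance as known reactions to Acthar, and both correspond to Section 15.4.1 criteria. The infection criterion has no condition that it be unmanageable. The FVC and FEV1 slopes (Section 20.3.2) would also lose their later data. Imputation is left to a separate SAP (Section 20.11.1), but no SAP can recover scores that were never collected.

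**Working it through.** **1. The plan's own figure (Section 20.10).** Inputs: 140 and 70 mITT subjects, 20% dropout, declines of 6.3 and 9, SD 5.83, two-sided 0.05.

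- Week 36 completers: 140 × 0.8 = 112 and 70 × 0.8 = 56. Difference: 9 − 6.3 = 2.7.
- SE = 5.83 × √(1/112 + 1/56) = 0.954, and 2.7/0.954 = 2.83.
- Power = Φ(2.83 − 1.96) = 0.808 (normal), or 0.803 with the noncentral t.

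The stated power of at least 80% is reproduced. By the t calculation it drops below 80% at 21% loss. This shows only that there is little reserve.

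**2. The two sections side by side.** The Adverse Event rule names study participation, so it needs no interpretation. In the cross-reference to Section 15.4.1, the noun discontinuation has no object. Its place in a list of reasons for leaving the study, directly after a sentence about leaving the study, favours study exit. The heading and rule of Section 15.4.1 favour a drug stop only. Section 15.4.1 then describes later contact only for "Subjects who early terminate from the Randomized Treatment Period for any reason other than withdrawal of consent", so it sets no schedule for a subject who is off drug but still in the study.

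**3. When the last required assessment falls.** Inputs: doses twice weekly for 2 weeks, then once in the third week (Section 15.4.1); Follow-up Visit 28 ± 2 days after the final dose (Section 14.12); Week 36 ± 5 days (Table 7-1). Assumptions: the Early Termination visit is on the day of the stop, the taper starts at once, and the last taper dose is on taper day 15 to 21.

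- The Follow-up Visit is 15 + 26 = 41 to 21 + 30 = 51 days after the stop, nominally 3 + 4 = 7 weeks.
- The Week 36 window is day 252 ± 5, that is, days 247 to 257.
- For a stop at week s, the Follow-up Visit can fall in the window if 7s + 51 ≥ 247 and 7s + 41 ≤ 257. So 7s is 196 to 216 and s is 28.0 to 30.9.
- The Early Termination visit falls in the window if 7s ≥ 247, so s ≥ 35.3.

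For stops before Week 28.0, nothing required falls in the window. From about Week 30.9 to 35.3 the same holds, but the Early Termination and Follow-up visits then lie on either side of Week 36.

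**4. Assessments affected.** Counts come from Table 7-1, for a subject who would not enter the extension. The Follow-up Visit is counted on both sides. The required 2 are Early Termination and Follow-up.

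| Stop just after | Follow-up Visit, week (range) | Telephone ALSFRS-R time points after it | Spirometry: scheduled → required | Investigator ALSFRS-R: scheduled → required |
|---|---|---|---|---|
| Week 4 | 11 (9.9–11.3) | 7 (Weeks 12 to 36) | 8 + 1 = 9 → 2 | 3 + 1 = 4 → 2 |
| Week 12 | 19 (17.9–19.3) | 5 (Weeks 20 to 36) | 6 + 1 = 7 → 2 | 2 + 1 = 3 → 2 |
| Week 24 | 31 (29.9–31.3) | 2 (Weeks 32 and 36) | 3 + 1 = 4 → 2 | 1 + 1 = 2 → 2 |

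The telephone counts are the same at both ends of each range. For a stop after Week 24 the number of investigator ratings does not change, but the last one comes at about Week 31 instead of at the Follow-up Visit after Week 36.

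**5. Calls already encouraged.** From Week 11 to Week 36 is 25 weeks, and 25/4.35 = 5.7, or about 6 monthly calls.

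**The case against.** The strongest reply is that an off-drug path already exists. Every early terminator who has not withdrawn consent is to be encouraged to continue, and what is collected is the ALSFRS-R by telephone at close to the four-weekly rhythm of Table 7-1. A reader might infer that the protocol abandons these subjects. It does not. What remains is the difference between encouraged and default, and the missing end week.

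A reader might also infer that every Section 15.4.1 drug stop certainly ends participation. The text does not settle this. The placement favours that reading, but a drug-only reading is open, and sites could apply the sentence differently. Pregnancy may look like a further conflict, since Section 21.5 stops treatment while Sections 18.8 and 22.1 withdraw the subject. These are compatible, because withdrawal includes stopping treatment.

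Section 14 says that telephone procedures go ahead on schedule when a subject cannot come to the site. It does not say that it covers early terminators, who have their own softer rule, so it does not close the gap.

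Finally, the plan already allows for 20% dropout, and the counts above are time points that rest on optional calls. They are not missing values. That is correct, and it limits the claim.

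**Conclusion.** The point holds as a weakness in data collection that is cheap to mend. Section 22.1 ends participation for an unacceptable-risk AE, and on its most natural reading for Section 15.4.1 stops. For stops before about Week 28, the subject's Week 36 primary score then depends on optional contact. The timing rests on the visit and taper assumptions stated above.

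A reader might go further and infer that the primary result will be biased or the trial underpowered. The documents do not support that. They give no rate of such stops for this trial and no off-drug course, and the separate SAP that will set imputation is not in the file. The pilot had 3 AE withdrawals in the low-dose and 7 in the high-dose group among 43 subjects (Sections 9.1 and 9.4). It was open label and mixed four regimens, so it shows only that such exits occur. The change should be made, but the primary analysis is not invalid without it. Confidence is medium, mainly because of the ambiguous cross-reference.

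**What to change.** For the Randomized Treatment Period only:

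- **Section 22.1.** State that meeting a Section 15.4.1 criterion, or an AE that makes study drug an unacceptable risk, ends study drug only. Keep the authority of the investigator, sponsor or medical monitor to end participation when participation itself is the risk. The Investigator Judgment entry alone would not preserve the sponsor's and monitor's part. All Section 15.4.1 stopping rules stay unchanged.
- **Safety visits.** State that the taper and the Early Termination, End of Taper and Follow-up assessments remain required after a drug stop.
- **Sections 15.4.1 and 22.1.** Replace the instruction that subjects "should be encouraged to continue minimal study participation via telephone contact" with a default: subjects off drug who have not withdrawn consent have the telephone ALSFRS-R at the remaining Table 7-1 time points through Week 36. Offer other in-person efficacy visits without requiring them, since a heavier schedule could prompt withdrawal of consent.
- **Section 12.1.1.** Require in extension criterion 1 that the Week 36 completer is on study drug, so that an off-drug subject followed to Week 36 does not qualify.
- **Section 20.4.4 or the SAP.** Record and summarise off study drug and off study as separate dispositions.

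The cost is amendment wording, one eCRF field, one more disposition summary and a few more telephone calls. The most is 7 assessments after the Follow-up Visit for a stop just after Week 4, against about 6 calls already encouraged.

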23 STUDY SUSPENSION, TERMINATION, AND COMPLETION

The sponsor may suspend or terminate the study or part of the study at any time for any reason. If the investigator suspends or terminates the study, the investigator will promptly inform the sponsor and the IRB/IEC and provide them with a detailed written explanation. Upon study completion, the investigator will provide the sponsor, IRB/IEC, and regulatory agency with final reports and summaries as required by regulations. Study termination and follow-up will be performed in compliance with Mallinckrodt standard operating procedures.

24 PROTOCOL AMENDMENTS

Any change in the study plan requires a protocol amendment. An investigator must not make any changes to the study without IRB/IEC and sponsor approval except when necessary to eliminate apparent immediate hazards to the subjects. A protocol change intended to eliminate an apparent immediate hazard to subjects may be implemented immediately, but the change must then be documented in an amendment, reported to the IRB/IEC within 5 working days, and submitted to the appropriate regulatory agency in the required time frame.

25 QUALITY CONTROL AND ASSURANCE

The sponsor performs quality control and assurance checks on all clinical studies that it sponsors. Before enrolling any subjects in this study, sponsor personnel and the investigator review the protocol, the Investigator's Brochure, the eCRFs and instructions for their completion, the procedure for obtaining informed consent, and the procedure for reporting AEs and SAEs. A qualified representative of the sponsor will monitor the conduct of the study.

25.1 Study and Study Site Discontinuation Criteria

The sponsor, investigator, or local and national regulatory authorities may discover conditions during the study that indicate that the study or study site should be terminated. This action may be taken after appropriate consultation between the sponsor and investigator. Conditions that may warrant termination of the study/study site include, but are not limited to:

- The discovery of an unexpected, serious, or unacceptable risk to the subjects enrolled in the study.
- The decision on the part of the sponsor to suspend or discontinue testing, evaluation or development of the IMP.
- Failure of the investigator to enroll subjects into the study at an acceptable rate.
- Failure of the investigator to comply with pertinent regulations.
- Submission of knowingly false information from the study site to the sponsor, study monitor, or local and national regulatory authorities.
- Insufficient adherence to protocol requirements.
- Study/study site termination and follow-up will be performed in compliance with Mallinckrodt standard operating procedures.

26 DIRECT ACCESS, DATA HANDLING, AND RECORD-KEEPING

26.1 Investigator

The investigator will permit study-related monitoring, audits, IRB/IEC review, and regulatory inspections by providing direct access to original source data and documents.

All subject information recorded in the eCRF will be attributable to source data from the investigational site. Each subject's eCRF should be fully completed and submitted to the sponsor in a timely manner.

If an investigator retires, relocates, or otherwise withdraws from conducting the study, the investigator must notify the sponsor to agree upon an acceptable storage solution. Regulatory agencies will be notified with the appropriate documentation.

Any significant changes in study personnel will require an updated Statement of Investigator (ie, FDA form 1572) to be filed with the sponsor.

The investigator must notify their IRB/IEC of protocol deviations in accordance with local regulatory and IRB/IEC requirements.

26.2 Sponsor

The eCRF data are stored in a database and processed electronically. The sponsor's MM reviews the data for safety information. The data are reviewed for completeness, and logical consistency. Automated validation programs will identify missing data, out-of-range data, and other data inconsistencies. Clinical laboratory data will be processed electronically. Requests for data clarification are forwarded to the study site for resolution.

27 SUBJECT INJURY

In general, subject to specific provisions in the clinical trial agreement, if a subject is injured as a direct result of an investigational medicinal product, the sponsor will pay for reasonable and necessary medical treatment for the injury, to the extent that such expenses are not covered by the subject's medical insurance, a government program, or other responsible third party. If laws or regulations of the locality in which the study is taking place require additional payment of expenses, the sponsor shall comply with such laws or regulations. Where applicable, the sponsor has taken specific national insurance.

28 RECORDS RETENTION

The investigator shall retain and preserve 1 copy of all data collected or databases generated in the course of the study, specifically including but not limited to those defined by GCP as essential. Essential documents should be retained until at least 2 years after the last approval of a marketing application in an ICH region and until there are no pending or contemplated marketing applications in an ICH region or at least 2 years have elapsed since the formal discontinuation of clinical development of the investigational medicinal product. These documents should be retained for a longer period, however, if required by the applicable regulatory requirements or by an agreement with the sponsor. It is the responsibility of the sponsor to inform the investigator/institution as to when these documents no longer need to be retained. Prior to destruction of any study essential documents, the investigator must first obtain written approval from the sponsor.

[REDACTED]

[REDACTED]

30 PUBLICATION POLICY

30.1 Sponsor's Publication Policy

The sponsor's policy is to publish or otherwise communicate the results of its hypothesis-testing clinical studies, regardless of outcome, for marketed products, compound(s) or product(s) being investigated that are later approved for marketing. Hypothesis-testing clinical studies are those studies intended to provide meaningful results by examining prestated questions using predefined statistically valid plans for data analysis, thereby providing firm evidence of safety and/or efficacy to support product claims.

Exploratory studies, in contrast, serve to set direction for possible future studies. They have significant statistical limitations, provide only preliminary information about a disease, condition, or product, and are not designed to provide final conclusions on product claims. The sponsor does not commit to publish or otherwise communicate the results of every exploratory study, because this information is of an exploratory nature and often highly

proprietary. However, if information from an exploratory study is of significant medical importance, the sponsor will publish or otherwise communicate the results.

The sponsor's decision to publish or otherwise publicly communicate the results of this study will be made in accordance with all applicable laws, regulations, and sponsor policies regarding publication and communication of clinical study results.

30.2 Investigator's Ability to Publish

Terms and provisions of publication rights are governed by the Publication Section in the clinical trial agreement.

32.1 Attachment 1: Clinical Laboratory Tests

Serum Chemistry	
Alanine aminotransferase (ALT)	Chloride
Albumin (total)	Creatinine
Alkaline phosphatase	Glucose
Aspartate aminotransferase (AST)	Phosphorus
Bilirubin (total)	Potassium
Blood urea nitrogen	Protein, total
Calcium	Sodium
CO ₂	Uric acid
Lipid Panel	
Total Cholesterol	LDL
Triglycerides	HDL
Diabetes Screen	
Hemoglobin A1c	
Hormones	
Serum and urine beta-human chorionic gonadotropin (pregnancy test)	
Hematology Assays	
Hematocrit	Platelet count
Hemoglobin	Red blood cell count
White blood cell count, including differential	Absolute neutrophil count
Urinalysis	
Blood	Nitrite
Color, clarity	Protein
Glucose	pH
Leukocyte esterase	Specific gravity
Ketones	
Hepatitis Serology	
Hepatitis B core antibody	Hepatitis C virus antibody (HCV)
Hepatitis B surface antigen	Hepatitis C virus PCR (only if HCV +)
TB Assay	
Interferon gamma release assay (IGRA)
